7.3. Other endpoints and outcome measures

The following exploratory analyses will be performed based on initial immunogenicity assessment and sample availability:

- Detailed analysis of cognate CD4+/CD8+ T cell function and memory phenotype may also be performed by multi-colour flow cytometry to simultaneously analyse surface markers and intracellular production of other cytokines (e.g. IL-2, IFNy, TNF α). Frequencies of 5T4-specific immune responses will be summarised in tabular format for each study arm and for overall combined study. Descriptive statistical analysis will be conducted, and the continuous variables will be summarised using mean, standard deviation, median, minimum and maximum. Fisher's exact test will be used to compare the 5T4-specific T cell response rates between study arms.
- Up-regulation of PD-L1 expression in a primary tumour or metastatic lesion(s) following study treatment. Density of PD-L1 positive immune cells and epithelial cells will be assessed by immunohistochemistry and digital image analysis of matched tumour tissue specimens before and after study treatment. PD-L1 expression levels will be summarised in terms of means, standard deviations and ranges for each study arm.
- PSA related kallikreins level change secondary to study treatment. The level of kallikreins in the blood will be measured by a 4 kallikrein peptidases test⁴⁵. Descriptive statistical analysis will be conducted.
- Change in number of circulating tumour cells secondary to study treatment may be assessed by CellSearch or Adnatest⁴⁴.
- Immunologic antigen spreading to other prostate associated antigens following study treatment (metastatic PCa patients only). The detection of antigen spread to other prostate associated antigens and the identification of specific antigens recognized will be analyzed descriptively by IFNy ELISPOT assay or ELISA.

Additional assays may include but are not limited to:

- Treatment-induced cellular immune responses characterized by cultured ELISPOT assay
- Treatment-induced cellular immune responses characterized by T cell receptor sequencing
- Flow cytometry analysis of immune cells isolated from the blood and surgical specimens

- Measurement of anti-5T4 serum antibody levels by ELISA (using plasma from preparation of above PBMC sample)
- Profiles of gene expression in the blood and surgical specimens by RNA analysis
- DNA or RNA sequencing of blood and tumour specimens for identification of tumour-specific somatic mutations

8. SAFETY ASSESSMENT

8.1. Specification, timing and recording of safety parameters

At regular intervals (specified in section 6.1), the subjects will be assessed for the following safety parameters:

- General physical examination and vital signs
- Full blood count
- Urea and electrolytes
- Liver function tests
- Kidney function tests

The above will be recorded in the patients' case report form (CRF) by the relevant clinician or their nominee.

Reports of recorded events, along with a narrative from the Chief Investigator, will be submitted to the Safety Monitoring Committee after every 6 completed patients.

8.2. Assessment of Adverse Events

Adverse Event (AE)

An AE is any untoward medical occurrence in a volunteer, which may occur during or after administration of an Investigational Medicinal Product (IMP) and does not necessarily have a causal relationship with the intervention. An AE can therefore be any unfavourable and unintended sign (including an abnormal laboratory finding), symptom or disease temporally associated with the study intervention, whether or not considered related to the study intervention.

Adverse Drug Reaction (ADR)

An AR is any untoward or unintended response to an IMP. This means that a causal relationship between the IMP and an AE is at least a reasonable possibility, i.e., the relationship cannot be ruled out. All cases judged by the reporting medical Investigator as having a reasonable suspected causal relationship to an IMP (i.e. possibly, probably or definitely related to an IMP) will qualify as adverse reactions.

Unexpected Adverse Reaction (UAR)

An adverse reaction the nature and severity of which is not consistent with the product information set out in:

- the summary of product characteristics (SmPC) for products with a marketing authorisation, i.e. nivolumab.
- the Investigator's Brochure (IB) for any other investigational product, i.e. ChAdOx1.5T4, MVA.5T4

Serious Adverse Event (SAE)

An SAE is an AE that results in any of the following outcomes, whether or not considered related to the vaccine:

- Death (apart from death where prostate cancer is certified as the underlying cause)
- Life-threatening event (i.e., the volunteer was, in the view of the Investigators, at immediate risk of death from the event that occurred). This does not include an AE that, if it occurred in a more serious form, might have caused death
- Persistent or significant disability or incapacity (i.e. substantial disruption of one's ability to carry out normal life functions)
- Hospitalisation, regardless of length of stay, even if it is a precautionary measure for continued observation or prolongation of existing hospitalisation
- An important medical event (that may not cause death, be life threatening, or require hospitalization) that may, based upon appropriate medical judgment, jeopardize the participant and/or require medical or surgical intervention to prevent one of the outcomes listed above. Examples of such medical events include allergic reaction requiring intensive treatment in an emergency room or clinic, blood dyscrasias, or convulsions that do not result in inpatient hospitalization.
- Congenital anomaly or birth defect

Serious Adverse Reaction (SAR)

An adverse event (expected or unexpected) that is both serious and, in the opinion of the reporting Investigator or Sponsors, believed to be possibly, probably or definitely due to an IMP or any other study treatments, based on the information provided.

Suspected Unexpected Serious Adverse Reaction (SUSAR)

A serious adverse reaction, the nature and severity of which is not consistent with the information about the medicinal product in question set out in the IB or SmPC.

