Checkpoint inhibitor treatment is associated with immune-mediated adverse reactions which may affect any organ system. Current data on the incidence of immune-related toxicities are derived from a number of large phase III clinical trials administering weeks to months of continuous checkpoint inhibitor therapy until disease progression, loss of clinical benefit or unacceptable toxicity, in a range of non-prostate tumour types. This study, however, will make use of a **restricted course of treatment limited to 3 infusions 4 weeks apart for metastatic PCa patients and only 1 infusion for low- or intermediate- risk PCa patients**. The incidence and severity of immune-mediated toxicities following a limited course of 3 infusions four weeks apart is not publically available. However, immune-mediated adverse events may occur at any time from the onset of therapy or after completion of treatment and may not be dose-dependent. Most immune-related adverse reactions, however, are low in severity and resolve with appropriate management, though fatal cases have been reported.

The frequency and median time to onset for the major immune mediated toxicities from pooled phase III datasets are shown in Table 1. These data relate to continuous therapy regimes with repeat nivolumab infusions at 2 week intervals. The incidence of toxicities grade 3 or above is <2% for all organ systems. Importantly, more than 50% of immune-mediated toxicities develop after several weeks of continuous treatment, therefore the frequency and risk of treatment-related adverse events following a restricted course of 3 infusions in this study is anticipated to be considerably lower than during licenced clinical use.

Table 1. Immune mediated adverse events after continuous monotherapy with Nivolumab

Immune-mediated toxicity	Frequency (%) *		Median (range) time to onset (months)	Corresponding number of doses at median time of onset **
	Any severity	Grade 3 or above		
Rash	25.6	0.9	1.4 months(0.0-113.7)	3
Diarrhoea / Colitis	12.6	1.3	1.4 months (0.0-20.9)	3
Pneumonitis	3.0	0.8	3.3 months (0.0-19.6)	7
Liver dysfunction/ Hepatitis	6.4	1.8	1.9 months (0.0-10.4)	4
Renal dysfunction	2.7	0.5	2.3 months (0.0-18.2)	5
Endocrinopathy				
Thyroid disorders	8.5	<0.1	2.8 months (0.0-14.0)	6

Adrenal insufficiency	0.4	0.2		
Pituitary disorders	0.4	0.2		

* From pooled dataset n = 2227 (CA209066, CA209037, CA209067 trials) nivolumab 3mg/kg across tumour types

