Expectedness will be determined according to the Investigators' Brochure (ChAOx1.5T4 and MVA.5T4 vaccines) or the SmPC (nivolumab).

Reporting Procedures for SUSARs

The Chief Investigator will report all SUSARs to the MHRA and ethical committee(s) within required timelines (15 days for all SUSARs, unless life threatening in which case 7 days, with a final report within a further 8 days (total 15). The Chief Investigator will also inform all Investigators concerned of relevant information about SUSARs that could adversely affect the safety of participants. All SUSARs and deaths occurring during the study will be reported to the Sponsor.

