8.7. Data and Safety Monitoring Committee

A Data and Safety Monitoring Committee (DSMC) will be appointed to provide real-time safety oversight. It will consist of a consultant oncologist, a consultant physician with experience of vectored vaccine trials, a further member with statistical expertise and up to two further members with trial expertise, all of them independent of the study. The DSMC will review all SAEs at the meetings that will be convened following each interim safety report and a narrative from the Chief Investigator at the timepoints as below:

An interim safety report of all recorded events, along with a narrative from the Chief Investigator, will be submitted to the Data and Safety Monitoring Committee for review after the first 6 patients (3 patients with intermediate risk disease and 3 metastatic patients) complete the study treatment and have reached the 24-week timepoint for efficacy assessment. An updated report to the Data and Safety Monitoring Committee, covering all enrolled participants to date will then be triggered when every 6th subsequent participant has reached 24-week timepoint for efficacy assessment.

The DSCM has the power to terminate the study if deemed necessary following a study-related SAE.

The DSMC chair will be notified of SAEs if deemed possibly, probably or definitely related to study-related interventions within 24 hours of the investigators' being aware of their occurrence.

The chair of the DSMC will be contacted for advice and independent review in the following situations:

- Following any SAE deemed to be possibly, probably, or definitely related to the study vaccine.
- Any other situation where the Investigator feels independent advice or review is important.

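### The SAE definition drops deaths certified as prostate cancer with no exception for suspected treatment relation, so expedited review of such a death is not guaranteed

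*Protocol*

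**What the plan says.** Section 8.2 makes seriousness independent of causality: "An SAE is an AE that results in any of the following outcomes, whether or not considered related to the vaccine". The first outcome listed is then narrowed: "Death (apart from death where prostate cancer is certified as the underlying cause". The exclusion has no relatedness condition and no time limit from the last dose. The neighbouring criteria carry no such exclusion, for example "Life-threatening event (i.e., the volunteer was, in the view of the Investigators, at immediate risk of death" and "Hospitalisation, regardless of length of stay".

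Seriousness opens the later steps. Section 8.2 defines a serious adverse reaction as "An adverse event (expected or unexpected) that is both serious and, in the opinion of the reporting Investigator or Sponsors", believed at least possibly due to a study treatment, and a SUSAR is a serious reaction of an unexpected kind. Section 8.5 applies the 24-hour report to the Sponsor and Study Medical Monitor to SAEs. Section 8.7 gives the DSMC chair 24-hour notice of SAEs judged at least possibly related, and states: "The DSMC will review all SAEs at the meetings".

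Section 8.5 also provides: "All SUSARs and deaths occurring during the study will be reported to the Sponsor". No deadline is attached to the reporting of deaths.

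**The concern.** A rule meant to capture serious outcomes whatever their cause removes one class of death by its certified cause. In a man with metastatic disease, prostate cancer may be the certified underlying cause of a death that the investigator nevertheless thinks could be related to treatment. The definition does not say what happens then. Timing is a further difficulty: the 24-hour clock starts when the investigator becomes aware of the event, but the classification depends on a certificate that may not be available by then.

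Safety is a co-primary objective in both groups. Section 4.2.1 says this MVA.5T4 product has not been given to humans before, and section 4.6.4 says of immune-related reactions to checkpoint inhibitors "though fatal cases have been reported". At stake is prompt independent review of a possibly related death in a group of 24 men.

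**Working it through.** The plan states no figure on this point, so the check traces one case through the safety sections. The case is a Group 2 death that the investigator considers possibly related, with prostate cancer certified as the underlying cause, and with no earlier event that met another SAE criterion.

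**Step 1: expedited steps**

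| Step | Section | What triggers it | Guaranteed here? |
|---|---|---|---|
| SAE by the death criterion | 8.2 | Death not certified as prostate cancer | No |
| SAR or SUSAR | 8.2 | Serious and related | No |
| 24-hour report to Sponsor and Study Medical Monitor | 8.5 | SAE | No |
| 24-hour notice to DSMC chair | 8.7 | SAE at least possibly related | No |
| Report of death to Sponsor | 8.5 | Any death | Yes, but no deadline |

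**Step 2: routes that do not need SAE status**

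- Section 8.3 requires a causality assessment for every AE.
- Section 8.7 sends the DSMC a periodic report of all recorded events, with a narrative.

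Both work in practice only if the death is recorded as an AE. That depends on the recording rule in section 8.5: all AEs within 28 days of study treatment, and outside that window only those of grade 3. The text does not say grade 3 or above. Table 3 in section 8.4 makes death grade 5. SAEs are reported throughout the trial, so this limit affects a death only where the exclusion in 8.2 has already taken away SAE status.

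**Step 3: length of the period outside the window, Group 2**

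- Treatments at weeks 0, 4, 8, 12 and 16 (section 4.3). They are 4 weeks apart, so on the nominal schedule the 28-day windows join up.
- End of the all-AE window: 16 + 28/7 = week 20.
- Follow-up: 12 months (section 4.4), about 52 weeks.
- Outside the window: 52 − 20 = 32 of about 52 weeks, for a man who completes treatment. It is longer for a man who stops early.

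**Step 4: does that period matter?** Section 4.6.4 says immune-mediated events can arise after treatment has ended. Its Table 1 gives onset ranges reaching 19.6 months for pneumonitis and 10.4 months for hepatitis. Those data come from continuous two-weekly nivolumab, and the protocol expects fewer events with the short course. They show that late onset is possible, not how often it will occur here.

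**Step 5: could the periodic DSMC report replace expedited notice?** Sections 5.7 and 8.7 place the first report after 6 patients have completed treatment and reached week 24. Later reports follow each further sixth participant to reach week 24. A man who dies before week 24 does not count towards the trigger, although the updated reports cover everyone enrolled. The route exists, but its timing is set by accrual and not by the event.

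**Step 6: size.** One death in Group 2 is 1/24 = 4.2%. The documents do not allow an estimate of how many possibly related deaths would fall in the gap.

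**The case against.** The strongest reply is that other provisions leave only a small gap.

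- Causality assessment covers every AE, not only SAEs (8.3).
- The DSMC receives all recorded events, may be convened early for safety concerns (5.7), and its chair can be consulted whenever the investigator sees a need (8.7).
- The life-threatening, hospitalisation and important-medical-event criteria have no cancer exclusion. A recognised fatal toxicity will often qualify under one of them, in or out of hospital.
- All deaths go to the Sponsor, and available post-mortem reports are provided for all deaths (8.5).

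This narrows the point considerably. It rules out three stronger conclusions that a reader might infer:

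- **That these deaths escape all causality assessment and DSMC review.** The SAE definition alone does not have that effect. It takes the additional grade wording in 8.5, and then only outside the 28-day window.
- **That the DSMC can stop the trial only after a study-related SAE.** Section 8.7 gives that power in that situation but does not say it is the only one. Section 5.7 has the committee advise on continuing in the light of the accumulating data.
- **That the co-primary safety result is biased by SAE status.** The endpoint in section 7.1 is the incidence of adverse events by type and severity, not the number of SAEs. Deaths in Group 2 also enter overall survival (7.2).

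The reply does not supply what the exclusion takes away. Early convening and consultation of the chair are discretionary, the report of deaths to the Sponsor has no time limit, and the periodic report follows accrual. It is also fair to say that some exemption for progression deaths is reasonable. The fault lies in the test used, which ignores the investigator's view of relatedness.

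**Conclusion.** The point holds in a limited form and should be corrected. Applied as written, section 8.2 leaves a possibly treatment-related death that is certified as prostate cancer, and meets no other SAE criterion, without guaranteed SAR or SUSAR classification, 24-hour reporting or notice to the DSMC chair. For about 32 of 52 weeks in Group 2, the literal wording of 8.5 could also leave that death unrecorded as an AE, and so outside the causality assessment and the DSMC report.

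The first conclusion rests on the text alone. The second assumes that sites apply the grade 3 wording literally, although grade 3 or above may well have been intended. The number of deaths affected is unknown and could be nil; any one would be 4.2% of Group 2.

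**What to change.** Reconcile sections 8.2, 8.3, 8.5 and 8.7:

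1. **8.2 and 8.3:** replace the certificate test, so that every on-study death is recorded and assessed for causality.
2. **8.5:** exempt from expedited reporting only deaths that the investigator documents as disease progression with no reasonable possibility of relation to a study product. Set a deadline for reporting all deaths to the Sponsor.
3. **8.5:** outside the 28-day window, record events of grade 3 or above.
4. **8.7:** list all deaths, with cause and days since last dose, in each DSMC report.

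The cost is a wording amendment and some extra forms. If 15% to 40% of Group 2 died on study, which is an assumption and not a document figure, that would be 24 × 0.15 = 3.6 to 24 × 0.40 = 9.6, or about 4 to 10 forms. Many would describe progression deaths and tell the committee little. The revised exemption still relies on investigator judgement, so a toxicity that nobody recognises could miss expedited reporting. It would, however, be recorded, assessed and listed for the DSMC.

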8.3. Causality assessment

For every AE, an assessment of the relationship of the event to the administration of the study treatments will be undertaken by the CI-delegated clinician. An intervention-related AE refers to an AE for which there is a probable or definite relationship to administration of a vaccine or checkpoint inhibitor. Adverse events are considered unrelated if they fall into the category of no relationship or unlikely relationship. An interpretation of the causal relationship of the intervention to the AE in question will be made, based on the type of event; the relationship of the event to the time of vaccine or checkpoint inhibitor administration; and the known biology of the vaccine and checkpoint inhibitor therapy (Table 2). Alternative causes of the AE, such as the natural history of pre-existing medical conditions, concomitant therapy, other risk factors and the temporal relationship of the event to study treatments will be considered and investigated.

Table 2. Guidelines for assessing the relationship of vaccine administration to an AE

0	No Relationship	No temporal relationship to study product and Alternate aetiology (clinical state, environmental or other interventions); and Does not follow known pattern of response to study product
1	Unlikely relationship	Unlikely temporal relationship to study product; and Alternative aetiology likely (clinical state, environmental or other interventions); and Does not follow known typical or plausible pattern of response to the vaccine
2	Possible	Reasonable temporal relationship to study product; or Event not readily produced by clinical state, environmental or other interventions; or Similar pattern of response to that seen with other vaccines
3	Probable	Reasonable temporal relationship to study product; and Event not readily produced by clinical state, environment, or other interventions or Known pattern of response seen with other vaccines
4	Definite	Reasonable temporal relationship to study product; and Event not readily produced by clinical state, environment, or other interventions; and Known pattern of response seen with other vaccines

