4.6.4 Risks associated with checkpoint inhibitor therapy

Extravascular infiltration

In the event of inadvertent infiltration into the extravascular compartment subjects may experience localised irritation and discomfort, including swelling and erythema. However, nivolumab (Opdivo®) is a non-vesicant drug and therefore does not confer risk of extravasation tissue necrosis. No specific neutralising or dispersal interventions are indicated. The potential for extravascular infiltration will be minimised by careful selection of the cannulation site and close monitoring of the subject during the infusion. At the earliest appearance of extravascular infiltration the infusion will be stopped, the device removed and the site cared for according to local guidance.

Infusion reaction

At the time of licencing the overall incidence of hypersensitivity/infusion reactions associated with nivolumab monotherapy was 5.0%. The majority of infusion reactions are mild in severity and are evident within 2 hours of the infusion. Hypersensitivity reactions may manifest as:

- Flushing or itching or rash
- Nausea or vomiting
- Fever or chills
- Dyspnoea, wheeze or chest discomfort
- Hypotension and changes to vital signs

All infusion reactions will be graded and recorded as adverse events according to NCI CTCAE v4.0 criteria and managed in line with established site-specific treatment algorithms. All treatments will be undertaken by oncology nurses experienced in the management of intravenous therapies and take place in a treatment facility with access to resuscitation equipment and a medical emergency / resuscitation team. Severe infusion reactions and anaphylaxis will be managed according to Advanced Life Support protocols.

General side effects

The most frequent side effects of immune checkpoint inhibitor therapy are fatigue, decreased appetite and nausea which each affect between 20 and 50% of cancer patients receiving continuous checkpoint inhibitor treatment in recent Phase III clinical trials. There is limited data on the side effects of short term immune checkpoint inhibitors.

Immune mediated toxicity

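### Section 8.3 gives a Possible adverse event no class, against 8.2 and 8.7, and Table 2's vaccine-only pattern test downgrades some nivolumab events

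*Protocol*

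**What the plan says.** **Threshold for related.** Section 8.3 states: "An intervention-related AE refers to an AE for which there is a probable or definite relationship to administration of a vaccine or checkpoint inhibitor". It continues: "Adverse events are considered unrelated if they fall into the category of no relationship or unlikely relationship". Table 2 has five grades: No, Unlikely, Possible, Probable and Definite.

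Section 8.2 includes Possible. Among the events counted as adverse drug reactions are those with a reasonable suspected causal relationship, "i.e. possibly, probably or definitely related to an IMP) will qualify as adverse reactions". The serious adverse reaction definition uses the same three grades: "believed to be possibly, probably or definitely due to an IMP or any other study treatments".

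Section 8.7 includes Possible as well: "The DSMC chair will be notified of SAEs if deemed possibly, probably or definitely related to study-related interventions". Its separate list of situations for chair advice and independent review uses the three grades but names one product only: "Following any SAE deemed to be possibly, probably, or definitely related to the study vaccine".

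**Pattern criterion.** The text of 8.3 tells the assessor to weigh the known biology of both the vaccine and the checkpoint inhibitor, and cites Table 2 for this. The table's title mentions vaccine administration only. Row 0 (No) refers to the study product. Row 1 (Unlikely) refers to the vaccine. Row 2 (Possible) refers to a pattern similar to other vaccines. Rows 3 and 4 (Probable and Definite) both use: "Known pattern of response seen with other vaccines".

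**The concern.** Safety of the vaccine combined with anti-PD-1 is a co-primary objective in both groups. Section 4.6.4 says that toxicity data for a limited three-infusion course are not publicly available, so this trial's causality grades carry information of their own.

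Two faults interact. The first is a contradiction: the same Possible event is an adverse reaction under 8.2 and not intervention-related under 8.3, and 8.3 does not call it unrelated either. Two people tabulating related events from this protocol could produce different counts and both be following the text. The second is that nivolumab has its own immune-mediated toxicity pattern, set out in 4.6.4 and Table 1, but rows 1 to 4 of Table 2 give no credit for matching it. The second fault moves nivolumab events down a grade, and the first decides whether the lower grade still counts.

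**Working it through.** The protocol gives no figure to reproduce here. The check sets the definitions side by side and then works through Table 2 as a set of rules.

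**Step 1: where Possible falls**

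| Section | Term | Grades included | Status of Possible |
|---|---|---|---|
| 8.2 | Adverse reaction | Possible, Probable, Definite | In |
| 8.2 | Serious adverse reaction | Possible, Probable, Definite | In |
| 8.7 | Notification of DSMC chair | Possible, Probable, Definite | In |
| 8.3 | Intervention-related | Probable, Definite | Out |
| 8.3 | Unrelated | No, Unlikely | Out |

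**Step 2: Table 2 as rules.** Let T = reasonable timing, N = not readily produced by another cause, P = pattern criterion met.

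- Definite: T and N and P.
- Probable: the row mixes *and* with *or*, so two readings are possible. Reading A is T and (N or P). Reading B is (T and N) or P.
- Possible: T or N or P.
- Otherwise: Unlikely or No.

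For a nivolumab-pattern event that vaccines do not share, P fails as the table is written. The last column shows the grade if the nivolumab pattern were allowed to count.

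| T | N | Grade as written (A and B agree) | Related under 8.3 | Related under 8.2 | Grade if nivolumab pattern counted |
|---|---|---|---|---|---|
| yes | yes | Probable | yes | yes | Definite |
| yes | no | Possible | no | yes | Probable |
| no | yes | Possible | no | yes | Possible (A), Probable (B) |
| no | no | Unlikely/No | no | no | Possible (A), Probable (B) |

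Definite is out of reach in every row as written. In the second row the vaccine-only wording by itself changes the event from related to not related under 8.3. In the fourth row it also takes the event below the 8.2 and 8.7 thresholds. There row 1 is satisfied, because the event does not follow the vaccine's pattern. Row 0 is not, because the event does follow the pattern of a study product. The grade is therefore Unlikely.

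**Step 3: whether such events are realistic here.** Section 4.6.4 names competing causes for the main examples: infective enteritis or overflow for diarrhoea; metabolic or obstructive disease for liver toxicity; pre-renal causes, other nephrotoxic agents and obstructive uropathy for renal dysfunction, the last with particular reference to pelvic or retroperitoneal disease. So N will often be in doubt in Group 2. Section 4.6.4 also says immune-mediated events can appear at any time, including after treatment ends, so T may be doubted for late events.

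**Step 4: rough scale.** Any-severity rates in Table 1, applied to the 24 Group 2 men:

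- Diarrhoea/colitis: 24 × 0.126 = 3.0
- Liver dysfunction/hepatitis: 24 × 0.064 = 1.5
- Renal dysfunction: 24 × 0.027 = 0.6

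These are rates under continuous monotherapy, and the protocol expects considerably lower ones on three infusions. Only the events with a doubtful N or T would lose related status. The figures show that a few events are at issue; they do not estimate a bias.

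**The case against.** The case for leaving this alone has several parts, and much of it stands.

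- **The primary safety result does not use the 8.3 term.** Section 7.1 counts adverse events by type and severity with no causality filter, 9.2 presents frequency, severity and duration, and 8.5 records events within its reporting window whether or not they are attributed to study procedures. The protocol specifies no treatment-related table. A reader might infer that the combination will look safer than it is. The documents do not support that for the co-primary safety endpoint.
- **Oversight mostly bypasses 8.3.** All serious events go to the sponsor or its delegate and to the medical monitor within 24 hours regardless of cause, and the DSMC receives reports of all recorded events. The chair-review list also has a catch-all for any situation where the investigator wants independent advice.
- **A well-timed nivolumab event with no other ready cause still reaches Probable** and counts as related. Losing Definite has no consequence in 8.3, which treats the two grades alike.
- **The text of 8.3 points assessors to checkpoint inhibitor biology**, Table 2 is offered as guidance, and row 0 says study product. A careful assessor could partly correct for the wording.

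A stronger reading of size is also tempting. Section 4.6.4 says: "The most frequent side effects of immune checkpoint inhibitor therapy are fatigue, decreased appetite and nausea", each in 20 to 50% of patients. Applied to Group 2 this gives 24 × 0.20 = 4.8 to 24 × 0.50 = 12 men per symptom, and a reader might infer that all of them drop out of the related count. That does not hold. Section 4.6.3 lists fatigue and anorexia among possible vaccine reactions, and 6.1 solicits fatigue and nausea after the first vaccination, before any nivolumab, so these symptoms can meet the vaccine pattern and reach Probable. The rates also come from continuous therapy.

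What survives is the contradiction over Possible and the misgrading of nivolumab-pattern events that vaccines do not share and that have a competing cause or doubtful timing.

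**Conclusion.** The point holds in limited form. The threshold in 8.3 contradicts 8.2 and 8.7 on the face of the text and leaves Possible without a class. Rows 1 to 4 of Table 2 cannot recognise a nivolumab pattern. An event such as raised liver enzymes, diarrhoea/colitis or renal dysfunction is therefore capped at Probable, falls to Possible when another cause is plausible, and can fall to Unlikely when its timing is doubted as well. These results are the same under either reading of the Probable row.

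The effect is confined to causality grades, to any summary of treatment-related events, and, for serious events graded Unlikely, to the adverse reaction definition and chair notification. Total adverse event incidence and recording under 8.5 are untouched. No number of men affected can be derived from the documents. The conclusion assumes that assessors apply Table 2 as worded; where they follow the broader text of 8.3, the second fault shrinks, but the contradiction over Possible remains.

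**What to change.** Three changes of wording:

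1. In 8.3, define an intervention-related event as possible, probable or definite, matching 8.2 and 8.7. Possible then has a class, and the existing definition of unrelated can stay.
2. In Table 2, replace the references to the vaccine and to other vaccines, in the title and in rows 1 to 4, with the study product concerned: the Investigator's Brochure for ChAdOx1.5T4 and MVA.5T4, and the SmPC for nivolumab. These are already the reference documents for expectedness in 8.5. While the table is open, bracket the *and*/*or* in the Probable row.
3. In 8.7, reconcile the chair-review trigger, which names only the study vaccine, with the notification sentence, which covers all study-related interventions.

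Separate causality fields for vaccine and nivolumab are optional; same-day dosing limits how well the two can be told apart. The changes are textual. The downside is a higher reported rate of related events, which should be explained when the results are presented.
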